10.4.7 PLANNED INTERIM ANALYSES

10.4.7.1 SAFETY REVIEW

Administration of study agent will be halted when three serious AEs* determined to be "probably related" (i.e., with new onset during study patches/pills) are observed. The PI will immediately notify the DSMB when this occurs. The DSMB will notify the study sponsor and investigators immediately when the third severe event is reported and enrollment screens will stop accepting new study participants. The DSMB will request the statistical analyses and tables that they wish to review, and these will be prepared by an unblinded biostatistician associated with the study. All requested documentation will be provided to the DSMB. The DSMB will convene an ad hoc meeting by teleconference or in writing as soon as possible. The DSMB will provide recommendations for proceeding with or terminating the study to the PI and the NIH. The study sponsor will inform all appropriate regulatory agencies of the temporary halt and the disposition of the study (i.e., terminate, continue).

*Statistically, the most likely examples of serious adverse events in the present study include development of a venous thromboembolism or a suicide attempt during an experimental phase of the study.

10.4.7.2 EFFICACY REVIEW

There are no efficacy endpoints in the present study because this is not a treatment study and the intervention used is not expected to be an effective treatment for any condition.

10.4.8 ADDITIONAL SUB-GROUP ANALYSES

The study is not powered to conduct sub-group analyses, and therefore they will not be performed.

10.4.9 MULTIPLE COMPARISON/MULTIPLICITY

N/A

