Design Overview: 40 female patients (up to 60 enrolled to allow for dropout) with recent suicidal ideation but minimal^{17,18} imminent risk for suicide attempt will complete behavioral tasks and clinical risk assessments in **three** conditions: **(A) perimenstrual E2/P4 withdrawal** (under placebo), **(B) perimenstrual P4 withdrawal** (during exogenous perimenstrual stabilization of E2 only) and **(C) perimenstrual E2 withdrawal** (during exogenous perimenstrual stabilization of P4 only). Mediation by degree of perimenstrual ALLO withdrawal will be explored for significant condition contrasts.

CENTRAL HYPOTHESIS: Test the hypothesis that key suicide risk pathways will be heightened during conditions involving P4 withdrawal (conditions A and B above) relative to the E2 withdrawal condition (condition C), and that this greater risk will be mediated by a steeper slope of withdrawal from ALLO during P4 withdrawal and natural (placebo) E2/P4 withdrawal conditions relative to E2 withdrawal condition (where P4 is stabilized).

JUSTIFICATION OF E2/P4 DOSING AND SCHEDULE

Chosen formulations are bioidentical to human E2 and P4 and were selected to mimic luteal phase concentrations or E2 and P4. Results from the PI's recently-completed similar experiment indicate that these doses were effective in stabilizing (rather than increasing) luteal phase levels.

Rationale for Route and Dose of E2 and P4. We will use Climara® 7 day transdermal E2 patches. Peak levels of E2 with Climara (~45 pg/mL), achieved within 24 hrs., correspond to luteal E2 levels¹⁰². No transdermal P4 is available. Although transdermal synthetic progestins are available, these molecules have a high affinity for androgen and mineralocorticoid receptors, limiting their usefulness for testing hypotheses. Thus, oral prometrium will be dosed b.i.d. to achieve luteal P4 levels (~13 ng/dL)¹⁰² to create **steady-state levels**.

Rationale for Duration of E2/P4. Administration for 14 days starting 7 days after ovulation will span the range of time in which natural perimenstrual withdrawal would occur and prevent natural withdrawal of *either E2 or P4*.

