4.2.1 PRIMARY ENDPOINT

The primary endpoints (described below) of this mechanistic study are suicidal ideation and planning score differences between placebo condition and stabilization conditions on the SITBI measure. These were chosen given their strong predictive validity in epidemiological studies.

(1) Mean Within-Person Condition Differences (7 final placebo days – 7 final stabilization days) of SITB Suicidal Ideation subscale score

CLEAR 2 Study Protocol: Hormones and Suicide Risk, Version 9, 07-02-2020, Page 14 of 64

(2) Mean Within-Person Condition Differences (7 final placebo days – 7 final stabilization days) of SITB Suicidal Planning subscale score

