10.2 STATISTICAL HYPOTHESES

Hypotheses. For suicidal desire and suicidal action capacity—our primary endpoints)—we predict that perimenstrual increases in suicidal desire and action capacity (Lab 2 – Lab 1 within each condition) will be larger in the placebo (natural E2 + P4 withdrawal) condition and experimental E2 stabilization (P4 withdrawal) condition than in the experimental P4 stabilization (E2 withdrawal) condition. The associated null hypothesis is that there will be no difference in the perimenstrual increase in suicidality across conditions. For our secondary endpoints, including hopelessness, negative social appraisals, reduced inhibitory control, and threat sensitivity, we predict the same pattern of results.

There are no "efficacy" endpoints in the present trial since it is mechanistic and not a treatment study.

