10.4 DESCRIPTION OF STATISTICAL METHODS

10.4.1 GENERAL APPROACH

The design of this study is a three-period crossover design, where each of three study periods is a perimenstrual frame of the menstrual cycle (days +7 to +22 following ovulation where positive ovulation test day=0). Each participant will complete all three conditions in a randomized order.

Primary hypothesis tests will be evaluated using a alpha level of .05, with a two-tailed test.

All outcomes will be checked for normality; given the low likelihood that suicidality will follow a normal distribution even in this clinical sample, we expect that we will need to utilize nonparametric procedures.

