10.5 SAMPLE SIZE

An unlimited number of potential participants will be screened. 60 females will be enrolled in the study, with the goal of 40 participants completing the study.

Power analyses are described below; alpha is set at .05, power at 80%. The null hypothesis is no link between the study experimental condition and risk for suicidal ideation, intent, and planning; the alternate hypothesis is that hormone stabilization in the experimental condition will prevent flux in these suicide-related outcomes. Because no previous studies have examined the impact of experimental hormones on suicidality, we have conducted power analyses using existing effect sizes on related constructs (e.g., BPD features).

Power Analysis. For primary hypothesis tests, 80% power to detect a conventionally mediumsized effect of condition (f = .25) is achieved with 24 participants¹¹⁷. To allow for attrition and improve generalizability and power, we propose to include 40 participants in the final sample.

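### Section 10.4.9 marks multiplicity N/A despite two primary endpoints and three conditions; if either endpoint alone counts, the primary error rate is about 6.5% to 10%, not 5%

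*Combined protocol and SAP*

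**What the plan says.** - **Two primary endpoints.** Section 4.2.1: "The primary endpoints (described below) of this mechanistic study are suicidal ideation and planning score differences between placebo condition and stabilization conditions". Ideation and planning are listed separately, with no statement on whether one or both must succeed.
- **Error rate.** Section 10.4.1: "Primary hypothesis tests will be evaluated using a alpha level of .05, with a two-tailed test". No family-wise level is given. Section 10.5 also sets alpha at .05, with 80% power.
- **Three conditions, two predicted differences.** Section 10.4.1: "The design of this study is a three-period crossover design". The central hypothesis in section 2.2 is that "key suicide risk pathways will be heightened during conditions involving P4 withdrawal (conditions A and B above) relative to the E2 withdrawal condition". Section 10.2 likewise predicts larger increases under placebo and under E2 stabilization "than in the experimental P4 stabilization (E2 withdrawal) condition", while its null is the omnibus one of no difference across conditions.
- **Analysis.** Section 10.4.2 specifies one repeated measures ANCOVA of the condition effect per outcome, done the same way for the two primary and five secondary outcomes. It names no pairwise contrasts and no gatekeeping.
- **Multiplicity.** The section headed "10.4.9 MULTIPLE COMPARISON/MULTIPLICITY" contains only N/A. Section 10.1 says there will be no formal SAP, so no other document supplies a rule.

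**The concern.** N/A says that multiplicity does not arise. With two primary endpoints tested separately and a hypothesis spanning three conditions, it does. Nothing prevents a report from treating a significant result on ideation alone, or planning alone, as support for the central hypothesis, and the chance of a false claim then exceeds the 5% in section 10.4.1.

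The contrasts add to this. An omnibus test cannot by itself show that A and B each exceed C, so pairwise comparisons will be needed to answer the question. Section 2.2 already expects them, since mediation is to be explored where condition contrasts are significant. At stake is whether a claim that progesterone withdrawal drives perimenstrual suicide risk, which section 2.2 wants to use to identify intervention targets, carries the error rate a reader will assume.

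**Working it through.** **Inputs from the protocol.** Alpha .05 two-sided (10.4.1, 10.5); two primary endpoints (4.2.1); m = 3 conditions (10.4.1); contrasts A-C and B-C (2.2, 10.2); f = .25, 24 participants for 80% power, 40 completers (10.5).

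**Assumed, because the documents give neither.** The correlation r between the two endpoints (0 to .95) and the within-person correlation ρ among conditions (.3 to .6).

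**Step 1: the plan's own figure.** For a within-subject factor, λ = f²·N·m/(1−ρ), with m−1 and (N−1)(m−1) degrees of freedom. At N = 24 and ρ = .5, λ = .0625 × 24 × 3/.5 = 9 and power is 74.1%; 80% needs 28 participants. The need is 25 at ρ = .55 and 23 at ρ = .6, so 24 is reached only with an unstated ρ between .55 and .6. The calculation is for a single test at .05, with no allowance for a second endpoint.

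**Step 2: independent tests.**
- Two tests at .05: 1 − .95² = 9.75%.
- Four tests at .05: 1 − .95⁴ = 18.5%.

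**Step 3: correlated tests.** Simulation under the global null: 40 participants, three exchangeable conditions, normal scores, 100,000 trials for each r. Probability of at least one false success:

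| What counts as success | r = 0 | .5 | .7 | .9 | .95 |
|---|---|---|---|---|---|
| Either endpoint's omnibus test | 9.9% | 9.1% | 8.4% | 7.2% | 6.5% |
| Either contrast on either endpoint, only after that endpoint's omnibus test | 8.2% | 7.6% | 7.0% | 6.0% | 5.5% |
| Either contrast on either endpoint, ungated | 17.6% | 16.2% | 14.7% | 12.8% | 11.7% |
| Both contrasts, on either endpoint | 1.8% | 1.7% | 1.6% | 1.4% | 1.3% |
| Both endpoints' omnibus tests | 0.3% | 0.8% | 1.5% | 2.8% | 3.4% |

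The third row starts at 17.6% rather than 18.5% because A-C and B-C share condition C.

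**Step 4: a limit on the fourth row.** Those values hold when no condition differs. If A truly exceeds C with near-certain detection and B equals C, requiring both contrasts reduces to the B-C test on each endpoint. With either endpoint counting, the error can again approach 1 − .95² = 9.75%.

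**Step 5: power after a Bonferroni split.** With 40 completers, λ = .0625 × 40 × 3/(1−ρ) = 7.5/(1−ρ).

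| ρ | λ | Power at .05 | Power at .025 | N for 80% at .025 |
|---|---|---|---|---|
| .6 | 18.75 | 97.5% | 95.2% | 27 |
| .5 | 15.0 | 93.5% | 88.9% | 33 |
| .4 | 12.5 | 88.4% | 81.6% | 39 |
| .3 | 10.7 | 82.8% | 74.3% | 45 |

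**The case against.** **The hypothesis is worded conjunctively.** Sections 4.1 and 10.2 predict heightened risk in both A and B. Read as a success rule, this gives 1.3% to 1.8% under the global null. The wording does point that way, but it is a prediction and not a decision rule. It does not say whether both endpoints must succeed, and it does not protect against the partial null in step 4.

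**The plan names only omnibus tests.** This stands as a limit on the size. A reader might infer that the protocol delivers an 18% error rate. The documents do not support that: 12% to 18% requires four ungated contrasts that section 10.4.2 does not specify. For the tests it does specify, the ceiling is about 10%, and less if the endpoints are strongly correlated. Section 2.1 reports the same result for planning as for ideation in the preceding study, which gives no correlation but does not suggest a low one.

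**The two endpoints answer separate questions in a mechanistic study.** Ideation stands for desire and planning for action capacity, with different predicted mediators, and the protocol disclaims efficacy endpoints. Separate claims, each at .05, would be defensible if declared. But the protocol places both under one central hypothesis and does not declare them separate.

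**Planning scores may be sparse.** A reader might infer that planning is the endpoint most exposed to a chance finding, because recent concrete planning is an exclusion. The documents do not show this. In a null simulation with skewed scores (40 participants, 10,000 trials per setting), the omnibus false positive rate was 4.2%, 3.6%, 2.5% and 1.1% when 50%, 70%, 80% and 90% of participants always scored zero. Under that assumed shape sparsity makes the test conservative, and the rates in step 3 would be somewhat too high.

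**Conclusion.** The point holds in conditional form. The protocol sets a .05 level for primary tests, has two primary endpoints and three conditions, and declares multiplicity not applicable, so the family-wise error for the primary claim is not controlled at 5%.

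If either endpoint alone counts, the two planned omnibus tests give about 6.5% to 10%. If any ungated A-C or B-C contrast also counts, the figure is about 12% to 18%. Under the global null it is below 5% if both endpoints or both contrasts are required, but no such rule is written, and one chosen after the data are seen would not control the error.

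These figures assume normal scores, 40 completers and an endpoint correlation between 0 and .95. The protocol should be changed, because the remedy is cheap and bears on the primary claim.

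**What to change.** Replace N/A in section 10.4.9 with a pre-specified rule:

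1. Judge the omnibus condition tests on ideation and planning by Bonferroni (two-sided .025 each) or Holm.
2. Test A-C and B-C at that endpoint's level, and only if its omnibus test is significant. With three conditions this holds the error within each endpoint. The same gating applies if nonparametric tests are used.
3. Report the five secondary endpoints as supportive, without confirmatory claims.

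Bonferroni caps the error at 5% with the contrasts included. Holm loses less power and protects the two omnibus tests. If the contrasts are to share the same 5%, the second endpoint should move to .05 only after the first endpoint's omnibus test and both its contrasts are significant; otherwise the bound with a partial null on one endpoint is .025 + .05 = 7.5%. A declared co-primary rule requiring both endpoints is an alternative that needs no split of alpha.

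The text cost is one paragraph. The power cost under Bonferroni is small at a within-person correlation of .5 or .6. At .4 power is 81.6%, and at .3 it falls below 80% with 40 completers. The sponsor should state the correlation it assumes in section 10.5 and repeat the calculation at the level adopted.

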10.4.10 TABULATION OF INDIVIDUAL RESPONSE DATA

Individual response data will be tabulated only if requested by the DSMB.

10.4.11 EXPLORATORY ANALYSES

Not applicable.

10.5 SAMPLE SIZE

An unlimited number of potential participants will be screened. 60 females will be enrolled in the study, with the goal of 40 participants completing the study.

Power analyses are described below; alpha is set at .05, power at 80%. The null hypothesis is no link between the study experimental condition and risk for suicidal ideation, intent, and planning; the alternate hypothesis is that hormone stabilization in the experimental condition will prevent flux in these suicide-related outcomes. Because no previous studies have examined the impact of experimental hormones on suicidality, we have conducted power analyses using existing effect sizes on related constructs (e.g., BPD features).

Power Analysis. For primary hypothesis tests, 80% power to detect a conventionally mediumsized effect of condition (f = .25) is achieved with 24 participants¹¹⁷. To allow for attrition and improve generalizability and power, we propose to include 40 participants in the final sample.

10.6 MEASURES TO MINIMIZE BIAS

10.6.1 ENROLLMENT/ RANDOMIZATION/ MASKING PROCEDURES

Individuals will be enrolled following phone screen and an enrollment visit as described above. Individuals will be randomized by IDS to one of six condition orders (permutations of A-B-C) following enrollment visit if they meet study criteria and give informed consent. Masking and blinding will be handled by IDS according to standard procedures for double blinding, and will be

CLEAR 2 Study Protocol: Hormones and Suicide Risk, Version 9, 07-02-2020, Page 46 of 64

fully double-blind. Randomization codes will be kept by IDS until the completion of the study, and will be shared only as needed for unblinding as needed for safety monitoring (described above).

Blinding and Compliance: Pills are dispensed in a double-blind manner. Patches will be placed by CTSA staff at UIC. All study staff will remain blinded. Preliminary analyses from the preceding similar experiment revealed that the blinding was successful; participants were not more likely to report believing they were on active treatment in the active condition relative to the placebo condition (p = .58). Participants will: **1**) be educated on the importance of compliance; **2**) be asked about compliance on each daily call; and **3**) have steroid levels measured to confirm compliance.

10.6.2 EVALUATION OF SUCCESS OF BLINDING

At the conclusion of the study, each participant will be asked to guess which condition order they had. Blinding will be evaluated by determining whether the accuracy of these reports is greater than 50% (chance).

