Primary Windows of Comparison for Hypothesis Testing. To test whether prevention of P4 withdrawal (in Condition C) reduces the perimenstrual increase in suicide risk, **primary** hypothesis tests will compare degree of suicide risk (as measured with self-report, tasks, and interviews) during the perimenstrual weeks of each condition (days +7 to +22). **Secondary** analyses will examine Condition C, testing whether tapered withdrawal from exogenous P4 around days +16 to +22 causes "shifted"/"postponed" perimenstrual risk.

Hypotheses/Analytic Plan. It is hypothesized that Condition A (E2/P4 withdrawal under placebo) and Condition B (P4 withdrawal under E2 stabilization) will BOTH be associated with heightened perimenstrual suicidality, but that Condition C (E2 withdrawal under P4 stabilization) will significantly reduce perimenstrual increases in suicidality. We also hypothesize that a steeper slope of ALLO withdrawal, calculated across the lab ALLO measures in each condition, will mediate the more deleterious effects of P4 withdrawal conditions. Multilevel models will be used (repeated observations nested within individuals) to predict daily or weekly repeated suicidality and mediator outcomes from a within-person condition factor (and, if appropriate, the interaction of condition and day). Mediation by degree of ALLO withdrawal will be tested by estimating a 95% CI for the indirect effect of condition (focal predictor) on suicide risk outcomes (dependent variable) via the slope of ALLO change across the perimenstrual phase (mediator). **Power Analysis**. For primary hypothesis tests, 80% power to detect a conventionally medium-sized effect of condition (f = .25) is achieved with 24 participants¹¹⁷. To allow for attrition and improve generalizability and power, we propose to include 30 participants.

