7.3.2 ENROLLMENT/BASELINE

Following recruitment screening via telephone, interested individuals will schedule and attend an enrollment visit at which they will provide informed consent and be further assessed for eligibility, which includes assessment of self-reported inclusion/exclusion criteria (including appropriate level of suicide risk on the SITBI-- see information in section 5.1). If ineligible, they will be referred back to their mental health provider and receive payment for the enrollment visit. If eligibility is confirmed, they will be further characterized using the SCID-I and SCID-II and complete various psychosocial questionnaires. In addition, they will be trained in the protocol for urine ovulation testing, daily telephone assessments, and the patch/pill administration schedule. Participants will be randomized to one of six possible condition orders at that time.

The study agent will not be administered until Lab assessment 1 (i.e., not at this enrollment visit).

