7.3.4 FINAL STUDY VISIT

Debriefing visits will be scheduled within 15 days of study completion. In this final visit, a final risk assessment will be conducted and the participant will be referred as appropriate for additional clinical care. This final risk evaluation visit is included in order to reduce the likelihood of emergent risk following withdrawal from exogenous hormones in participants who had the placebo-experimental condition order. Participants will not be provided with individualized study results.

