7.4 JUSTIFICATION FOR SENSITIVE PROCEDURES

Placebo control is required to demonstrate unique effects (vs. expectancy effects) of hormones on indices of suicidality.

Ongoing Assessment of Suicidality

The PI ([name]) is a clinical psychologist with nine years of experience in risk assessment and empirically supported treatment of chronic suicidality (e.g., Dialectical Behavior Therapy); [name], whose office is adjacent to [name], is an experienced clinical psychiatrist with clear expertise in suicide risk assessment and management. These clinical qualifications will allow the PI and [name], the prescribing physician for the study, to carefully assess and manage any emergent changes in imminent suicide risk.

The available literature³ indicates that *participants in research studies do not generally become acutely upset in response to the psychological assessments conducted in the present study.* If participants do become upset during an assessment, they will be reminded of their right to discontinue participation, and mood changes or suicidality will be assessed and managed using the University of Washington Risk Assessment and Management Procedure (**UWRAP**), the suicide risk management protocol recommended by NIH in the context of RCTs for mood disorders.

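### The blinding check sets chance at 50%, but participants guess one of six condition orders, so chance is 1/6 and substantial unblinding could pass as intact blinding

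*Combined protocol and SAP*

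**What the plan says.** Section 10.6.2 describes the only blinding evaluation planned for this trial. At the end of the study, "each participant will be asked to guess which condition order they had". The criterion follows: "Blinding will be evaluated by determining whether the accuracy of these reports is greater than 50% (chance"). No test, sidedness or significance level is named, and the scoring of accuracy is not defined further.

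The number of possible orders is given twice. Section 10.6.1 says: "Individuals will be randomized by IDS to one of six condition orders (permutations of A-B-C"). Section 7.3.2 says: "Participants will be randomized to one of six possible condition orders at that time". Section 10.4.1 confirms a three-period crossover in which everyone receives all three conditions.

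One passage still reads as if there were two orders: section 7.3.4 explains the final risk assessment by reference to emergent risk "in participants who had the placebo-experimental condition order".

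**The concern.** A figure of 50% is the chance rate when there are two possible answers. Here the answer is one of six permutations. A benchmark set too high makes the check lenient: participants can do far better than guessing and still not exceed it.

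This matters because of the role the protocol gives to blinding. Section 7.4 says: "Placebo control is required to demonstrate unique effects (vs. expectancy effects) of hormones on indices of suicidality". The primary endpoints are suicidal ideation and planning as reported by participants in daily phone calls (sections 4.2.1 and 10.4.2). The central contrast sets Condition C against A and B, so recognition of the C cycle is the form of unblinding that would bear most directly on the main result. Section 10.4.4 lists dizziness in 24% and drowsiness in 9% of progesterone users, so some recognition is conceivable. Section 10.1 says there will be no formal SAP, so no later document is planned in which the benchmark would be put right.

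**Working it through.** **Inputs**
- Guess requested: the whole condition order, once, at the end (section 10.6.2).
- Possible orders: six (sections 7.3.2 and 10.6.1).
- Number guessing: 40, the completion goal (section 10.5).
- Test: none stated. I assume a one-sided exact binomial test at 5%.
- Allocation: the ratio is not stated. I assume equal allocation, or equivalently a uniform guess among the six orders.

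**Can 50% be reproduced?**
- Two conditions: 1/2! = 1/2 = 50%. This matches the stated figure but is not this design.
- Three conditions, whole order: 1/3! = 1/6 = 16.7%.
- Order guess scored period by period on the three-way label: a random permutation matches on average one of three periods, giving 1/3.
- Order guess scored period by period as placebo or active: the placebo position is right with probability 1/3 (all three periods match); otherwise one of three periods matches. That gives 1/3 + (2/3)(1/3) = 5/9 = 55.6%.

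Only a two-order design, or a separate active/placebo coin-flip guess for each period, gives 50%. Section 10.6.2 describes neither.

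**Critical values at n = 40**, the smallest r with P(X ≥ r | 40, p0) ≤ 0.05:
- p0 = 1/2: r = 26 (65%), tail 0.040.
- p0 = 1/6: r = 12 (30%), tail 0.026.
- p0 = 1/3 (position of C): r = 19 (47.5%), tail 0.044.

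At a one-sided 2.5% level the first two become 27 and 13, which changes nothing of substance.

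**Results that would be misread.** With 12 to 20 correct out of 40 (30% to 50%), accuracy is significantly above 1/6 but does not exceed 50% on any reading. With 21 to 25 correct, it is also missed if a significance test is intended. At 20/40, P(X ≥ 20 | 40, 1/6) = 1.2 × 10⁻⁶.

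**Two illustrative scenarios**
1. Everyone recognises C but cannot separate A from B. Once C is placed, two orders remain, so accuracy is 1/2.
2. Half recognise C in this way and the rest guess: 0.5 × 1/2 + 0.5 × 1/6 = 1/3.

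| Probability of flagging, n = 40 | Accuracy 1/2 | Accuracy 1/3 |
|---|---|---|
| Exact test against 50% (X ≥ 26) | 4.0% | 0.004% |
| Observed accuracy above 50% (X ≥ 21) | 43.7% | 1.0% |
| Exact test against 1/6 (X ≥ 12) | 99.7% | 73% |

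In the second scenario the position of C is identified with probability 0.5 × 1 + 0.5 × 1/3 = 2/3, and a test of that against 1/3 (X ≥ 19) flags it 99.6% of the time.

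**Sensitivity to n.** With true accuracy 50%, the test against 50% flags 3.2%, 4.9% and 4.6% of the time at n = 24, 30 and 60. The test against 1/6 flags 96.8%, 97.9% and 99.99%. The result does not depend on reaching exactly 40 completers.

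**The case against.** The strongest counter-argument is about weight. The check is one descriptive sentence, read once after the study ends. No endpoint, estimate, type I error, sample size or safety rule depends on it, and a reader given the raw accuracy and the six orders could apply 1/6 unaided. That is correct, and it limits the consequence to interpretation. It does not make the stated threshold right.

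Second, nothing in the documents shows that unblinding is likely. Placebos are described as identical in appearance, patches and pills are used in every condition, and in the preceding experiment participants were no more likely to report "believing they were on active treatment in the active condition relative to the placebo condition (p = .58"). The scenarios above are constructions, and the first falls exactly on 50%. They show what the rule would miss and do not forecast what will happen. The preceding result also concerned a two-way belief, so it does not validate a six-order guess.

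Third, the investigators may have intended a two-way item of that kind, for which 50% would be natural. If so, the question needs changing and the number could stay. As written, though, the question is about order.

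Fourth, correcting the benchmark does not make the check fully diagnostic. The protocol predicts that "Condition C (E2 withdrawal under P4 stabilization) will significantly reduce perimenstrual increases in suicidality", so participants may identify C through its effect. This stands, and it applies whichever benchmark is used.

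**Conclusion.** The concern holds. For the guess that section 10.6.2 describes, chance is 1/6 and the stated 50% is three times that. Used as written, the rule could report intact blinding when half the participants name their full order correctly, a result with p of about 1.2 × 10⁻⁶ against true chance.

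The value 1/6 rests on equal allocation or a uniform guess. The flagging rates also rest on 40 completers and a one-sided 5% exact test, none of which section 10.6.2 fixes; reasonable alternatives leave the conclusion unchanged. That the 50% was carried over from a two-condition design is plausible given the wording in section 7.3.4, but it is an inference and the conclusion does not need it.

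This should be corrected. It affects only how far expectancy effects can be judged, not the primary analysis.

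**What to change.** In section 10.6.2, replace 50% with 1/6 as the chance rate for a correct whole-order guess, and name the test: exact binomial, with its sidedness and level. If an active-versus-placebo belief was what the investigators meant to ask, reword the question and define its scoring so that benchmark and question agree.

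A useful optional addition from the same guess is the proportion of participants who place Condition C correctly, compared with 1/3, since C carries the main hypothesis. State alongside it that accuracy above chance may reflect a real effect of C as well as a failure of masking.

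The cost is one or two sentences and no new data, because the order guess is already planned. The downside is a stricter check, more likely to report unblinding that then has to be discussed.
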